8.3 Post-Treatment Efficacy and Safety Observations

While efficacy and safety observations will be listed regardless of whether the subject was taking blinded study drug, observations may not contribute to summaries/analyses if they are measured after the last dose of double-blind study medication as indicated below:

- all efficacy, clinical biomarkers and outcome research will be included in the analyses of double-blind period if measured on or prior to 28th day after the last dose date of lulizumab or matching placebo or on or prior to the 2nd day after the last dose date of BMS-986142 or matching placebo, whichever is latest. These windows are based on the four half-life times of each active medication (7 days for lulizumab, 11 hours for BMS-986142).

- all vital signs, pharmacokinetic, and immunogenicity assessments will be included in the analyses of double-blind period if measured on or prior to 21th day after the last dose date of lulizumab or matching placebo or on or prior to the 2nd day after the last dose date of BMS-986142 or matching placebo, whichever is latest. These windows are based on the three half-life times of each active medication (7 days for lulizumab, 11 hours for BMS-986142). These windows are different from the rest of the parameters because of the protocol visit schedule at 21 days since the end of the double-blind period.
- all adverse events will be included in the analyses of double-blind period if measured on or prior to 42th day after the last dose date of lulizumab or matching placebo or on or prior to the 3rd day after the last dose date of BMS-986142 or matching placebo, whichever is latest. These windows are based on the six half-life times of each active medication (7 days for lulizumab, 11 hours for BMS-986142).
- all safety laboratory and lipid parameter will be included in the analyses of double-blind period if measured on or prior to 28th day after the last dose date of lulizumab or matching placebo or on or prior to the 2nd day after the last dose date of BMS-986142 or matching placebo, whichever is latest. These windows are based on the four half-life times of each active medication (7 days for lulizumab, 11 hours for BMS-986142). These windows are different from the rest of the safety parameters because of the protocol visit schedule at 42 days since the end of the double-blind period.

8.3.1 Missing and Multiple Measurements

For listings of efficacy, safety, pharmacokinetic, biomarkers, immunogenicity, outcome research measures, missing values will be represented as not reported.

For all analyses and summaries of efficacy, safety, outcome research measures, missing values will not be imputed.

Some laboratory samples may be inadvertently analyzed multiple times for the same test, producing multiple lab results on the same collection date and time for the same subject. The selection of laboratory result for analysis for this subject will follow BMS global standard.

All blood pressure measurements will be included in the summaries/analysis independently of the position they were measured, e.g., sitting, supine, standing.

8.4 Assignment of Doses to Adverse Events and Laboratory Assessments

In case of missing dates and/or times, prior to assigning the treatment that the subject received at the onset of an AE or at the time of a laboratory assessment, imputation rules will be applied as follows:

For AEs, a missing or incomplete onset date will be imputed according to the following conventions:

- If the onset date for an AE is missing or incomplete, an imputed date will be derived to slot the event to an appropriate analysis period. This derived date will not be reported in summary tables or listings. Every effort will be made to determine the actual onset date for the event or to obtain a reliable estimate for the onset date from the investigator.

- If an onset date is missing, the derived onset date will be calculated as the first non-missing valid date from the following list (in order of precedence):
 - First active study medication date
 - Consent date
 - Visit date corresponding to the visit at which the event was reported.
 - If a valid non-missing date is not available for any of these dates, the derived onset date will be set to missing.
- If an onset date is incomplete, the derived onset date will be calculated using the following algorithm:
 - Calculate a surrogate date as the first non-missing valid date from the following list (in order of precedence):
 - ◆ First active study medication date
 - ◆ Consent date
 - ◆ Visit date corresponding to the visit at which the event was reported
 - ◆ If a valid non-missing date is not available for any of these dates, the surrogate date will be set to missing.
 - Based on the information provided, set the derived date to the earliest possible date. If only a year is provided, set the derived date to January first of that year. If a year and month is provided, set the derived date to the first day of that month.
 - If the surrogate date is non-missing then:
 - ◆ If the derived date is on or after the surrogate date use the derived date as calculated
 - ◆ If the derived date is prior to the surrogate date and the surrogate date is consistent with the partial data provided for the onset date, use the surrogate date as the derived date
 - ◆ If the derived date is prior to the surrogate date and the surrogate date is not consistent with the partial data provided for the onset date then set the derived onset date to be the latest possible date based on the partial onset date information provided. If only a year is provided, set the derived date to December 31st of that year. If a year and month is provided, set the derived date to the last day of that month.
 - If all three dates used to determine the surrogate date are missing, then based on the information provided, set the derived date to the earliest possible date. If only a year is provided, set the derived date to January first of that year. If a year and month is provided, set the derived date to the first day of that month.

A drug treatment file will be created, containing any starting and stopping dose as well as intermediate dose changes within each study period, with dates and times as recorded on the CRF. In this context,

- the date of the first dose of study medication is defined as the earliest start date with number of tablets > 0 or injections > 0 reported on the study medication page.
- the date of the last dose of study medication is defined as the latest start or stop date with number of tablets > 0 or injections > 0 reported on the study medication page.

- if a dosing time is missing for a starting dose of study drug in a study period or a dose change, then it is defaulted to 9:00.
- if there's a gap in the dosing information, then the dosing time corresponding to the start date of the gap, is defaulted to 00:00.

If a dosing time is missing for a last stop dosing date for the study drug in a study period, then it is defaulted to 23:59.

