7.4 Extent of Exposure

7.4.1 Study Therapy

The extent of exposure during the double-blind treatment period will be summarized for the As-treated analysis population in the following ways:

- by the number of days the subject is known to be on study drug, ignoring any dosing interruptions, using the formula below:

$$\text{Exposure (in days)} = (\text{date of last study medication}) - (\text{date of first study medication})$$

For Lulizumab or matching placebo, the date of last study medication corresponds to the last date of study medication + 7 days (the offset of 7 days represents the dosing interval of 7 days).

For BMS-986142 or matching placebo, the date of last study medication corresponds to the last date of study medication +1.

Because subjects receive either lulizumab or BMS-986142 together with the corresponding matching placebo for each medication

- the date/time of first study medication will be the earliest of the dates/times of first administration of BMS-986142 or Lulizumab or matching placebo.
- the date/time of last study medication will be the maximum of last study medication date/time as described above for each medication.

The frequency will be presented according to the duration ranges (in days) : 1-28, 29-56, 57-84 and ≥ 85 .

- by the number of Lulizumab or matching placebo study drug injections. The frequency will be presented using the following ranges in the total number of injections: 1-4, 5-8, 9-12, >12.
- by the number of BMS-986142 or matching placebo doses. The frequency will be presented using the same ranges as for the summary of number of days.

In addition to the frequencies mentioned above, the mean, standard deviation, median, minimum and maximum values will be summarized for all the above mentioned ways of summarizing extend of exposure.

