7.6.1 Adverse Events

All AEs are coded and grouped into Preferred Terms (PT) by System Organ Class (SOC), using the latest approved version of the Medical Dictionary for Regulatory Activities (MedDRA) at the time of database lock. Listings and summaries will be based on the resulting SOCs and PTs.

AEs will be included in the frequency tabulations if they occur while a subject is on study medication up to and including 42 days after the last dose of study medication of either active medications or matching placebos. These AE summaries will be based on proportions, which represent the number of subjects experiencing the AEs divided by the number of subjects received with at least 1 dose of study medication.

In summaries by SOC and PT, AEs will be sorted by decreasing frequency within each SOC and PT according to the Lulizumab group. In summaries by PT, AEs will be sorted by decreasing frequency within PT according to the Lulizumab group. Counting rules for adverse events are described in [section 8.18](#).

All adverse events listings will indicate the unique subject identifier, age, gender, current treatment, the date of onset, the date of resolution, day of onset relative to the start of treatment, action taken, investigator's assessment of severity and relationship to study drug.

Laboratory AEs are laboratory changes identified by the investigator as AEs and thus reported on the AE pages of the eCRF.

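### SAP 8.4 dates adverse events with a missing onset from the first active dose; read literally, this drops placebo events, but not active-arm events, from the summary tables

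*SAP*

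**What the plan says.** SAP section 8.4 gives the rule for adverse events whose onset date is missing or incomplete. Its purpose is stated: "an imputed date will be derived to slot the event to an appropriate analysis period".

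- **Wholly missing onset.** The derived date is the first available of: "First active study medication date", the consent date, the date of the visit at which the event was reported.
- **Incomplete onset.** The same three dates, in the same order, give a surrogate. The earliest date compatible with the partial entry is then compared with it: "If the derived date is on or after the surrogate date use the derived date as calculated". If it is earlier, and the surrogate fits the partial entry, "use the surrogate date as the derived date". If it is earlier and the surrogate does not fit, the latest compatible date is taken.

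The available SAP text does not define a first active date. Section 8.4 does define the first dose of study medication, as "the earliest start date with number of tablets > 0 or injections > 0 reported on the study medication page", but neither list uses that term. For exposure, section 7.4.1 takes the "earliest of the dates/times of first administration of BMS-986142 or Lulizumab or matching placebo".

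SAP section 7.6 admits an event to the summary tables only if its onset is no earlier than first dose.

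**The concern.** The word active decides the outcome. Elsewhere the SAP uses it to exclude placebo. Section 7.6.1 sets the adverse event window at "up to and including 42 days after the last dose of study medication of either active medications or matching placebos"; section 7.5.1 compares two active treatments with placebo; Appendix 1, item 7, concerns placebo subjects who are given active medication.

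On that usage a placebo subject has no first active date, and the next item, consent, takes its place. Consent is signed at screening, which may run to 28 days, or 35 with the extension, before Day 1. An event dated at consent therefore counts as pre-treatment and leaves the tables. The same event in an active arm is dated at first dose and stays. The error runs one way: it lowers placebo rates and so enlarges the apparent excess on lulizumab or BMS-986142. Safety is a secondary endpoint with about 25 subjects per arm, so a few misplaced events would be visible in the tables.

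**Working it through.** The plan states no figure on this point. The check applies the rule of section 8.4 with two surrogates: the consent date (placebo, literal reading) and the first dose date (active arms).

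**Worked dates.** An event is counted if its derived onset is not before first dose.

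| Consent | First dose | Onset recorded | Placebo, literal reading | Active arm |
|---|---|---|---|---|
| 6 March | 3 April | nothing | 6 March, not counted | 3 April, counted |
| 6 March | 3 April | year only | 6 March, not counted | 3 April, counted |
| 6 March | 3 April | March | 6 March, not counted | 31 March, not counted |
| 6 March | 3 April | April | 1 April, not counted | 3 April, counted |
| 6 March | 3 April | May | 1 May, counted | 1 May, counted |
| 10 May | 25 May | May | 10 May, not counted | 25 May, counted |

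For month-and-year entries the trigger is the calendar month of first dose. The March row has consent in the recorded month and shows no difference in counting. The April row does not, and shows one. If first dose falls on the 1st, the derived date equals first dose and the event is counted in every arm.

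**Share of on-treatment placebo events misplaced, literal reading.** Assumptions: first dose equally likely on each day of a 365-day year; true onset uniform over 84 + 42 = 126 days from first dose; consent 7, 14, 28 or 35 days before first dose. There are 365 × 126 = 45,990 combinations for each consent lag.

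- *Wholly missing:* always dated at consent, so 100%.
- *Month and year:* misplaced when onset falls in the month of first dose and first dose is on day d ≥ 2. In a month of L days this is the sum of (L − d + 1) for d = 2 to L, which is L(L − 1)/2: 465, 435 and 378 for 31, 30 and 28 days. Total 7 × 465 + 4 × 435 + 378 = 5,373, and 5,373 / 45,990 = 11.7%.
- *Year only:* misplaced when onset falls in the calendar year of first dose, unless first dose is on 1 January. With R days left in the year, min(126, R) onset days are affected, for R = 1 to 364. Total 239 × 126 + (125 × 126)/2 = 30,114 + 7,875 = 37,989, and 37,989 / 45,990 = 82.6%.

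The three shares are the same for all four consent lags. In the active arms all three are 0%.

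**Effect on a table row.** Section 7.6.1 divides subjects with the event by subjects dosed, planned at about 25 per arm. Section 8.18.1 counts a subject once per system organ class and selects one event per preferred term. Losing an event therefore changes a row only if that subject has no other qualifying event there; the change is then 1/25 = 4 percentage points, or 1/40 = 2.5 points if the study grows to 120 subjects.

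**After the fix.** With the surrogate set to first dose of any study medication, all three shares are 0% in every arm.

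**The case against.** The strongest reply is that the literal reading may not be the intended one. The one first-dose date that section 8.4 defines covers any tablet or injection, section 7.4.1 expressly includes matching placebo, and protocol section 4 counts placebo as study drug. If active was meant loosely, every dosed subject has the date, consent is never reached and the arms are treated alike. The SAP contains other wording foreign to this trial (dapagliflozin in Table 7.1.2-1, T1DM in section 8.1), so carried-over text is plausible, though that is an inference. This stands: a reader might infer that the plan deliberately dates events by treatment allocation, and the documents do not support that. They show an undefined term, one reading of which produces a bias by arm.

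There are also safeguards. Section 8.4 asks for every effort to obtain the real date first. Events before treatment stay in the listings and every serious event has a narrative (section 7.6.1.1). No between-group test is made on safety data (section 7.6). Non-serious events are collected only from first dose (protocol section 5.3), so a consent-date onset contradicts their collection window. These limit how often the problem arises and how far it reaches. They do not remove it: serious events are collected from consent, so the window gives no such check for them, and section 8.4 keeps derived dates out of tables and listings, so a reader would not see that an event had been moved.

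**Conclusion.** The point holds conditionally. On the literal reading, which matches the SAP's own use of active in sections 7.5.1 and 7.6.1 and Appendix 1, the rule misplaces all wholly missing placebo onsets, about 83% of year-only onsets and about 12% of month-and-year onsets, and none in the active arms. The last two shares rest on the uniform-date assumptions above. On the alternative reading the difference is nil.

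Three stronger inferences are not supported:

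- **That all incomplete placebo dates are affected, or those in the month of consent.** Onsets in months after first dose are handled identically in all arms, and the month that matters is that of first dose.
- **That each lost event costs 4 points.** That is a ceiling per affected subject and row at 25 per arm, reached only if the subject has no other qualifying event in the row.
- **That events vanish from the report.** They leave the summary tables only.

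The documents do not say how many onset dates will be missing or incomplete, so the total effect cannot be computed. The direction is known: any error lowers placebo rates. The wording should be corrected before database lock, so that the choice is not left to programming.

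**What to change.** In both lists of SAP section 8.4, replace the first item with: date of first dose of double-blind study medication (active or matching placebo), and refer to the definition of first dose already given in that section. Nothing else in the algorithm needs to change. The cost is a wording change in two places; no new data are needed and no efficacy analysis is affected.

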8.4.1 Treatment at Onset of an Adverse Event

Both onset date and (if requested) onset time of an AE will be compared to the dosing information. Treatment will then be the dose at the last observation for a subject in the dosing file where the AE onset date/time is not earlier than the dose date/time.

8.4.2 Treatment at the Time of a Laboratory Assessment

Laboratory draw date and time will both be compared to the dosing information. Treatment at the time of the laboratory assessment will then be the dose at the last observation for a subject in the dosing file where the laboratory date/time is not earlier than the dose date/time.

8.5 Non-study Medications

Start and stop date of all non-study medications are collected on the CRF. In order to classify medication as prior or concomitant, partial, missing or invalid start and stop dates will be imputed where possible as follows:

- If the reported start date is missing or invalid and the informed consent date is not missing or invalid, then the imputed start date is set equal to the informed consent date. If the consent date is missing or invalid and the birth date is not missing or invalid, then the imputed start date is set equal to the birth date. If the start date, the consent date and the birth date are all invalid or missing, then the imputed start date is set equal to missing.
- If the reported start date is partially entered, then the imputed start date is set equal to the earliest possible reported start date based on the partial entered reported start date.
- If the reported end date is missing, continuing, unknown or invalid, then the imputed end date is set equal to the most recent database extraction date.
- If the reported end date of the medication is partial, then the imputed end date is set equal to the last possible reported end date based on the partial entered reported end date.

Imputed dates will not appear on the listings of non-study medication.

8.6 EULAR Sjögren's Syndrome Disease Activity Index (ESSDAI)

The EULAR Sjögren's Syndrome Disease Activity Index (ESSDAI) total score is calculated as the sum of scores for activity level for each domain.³³ The scores and the domains are presented in [Table 8.6-2](#).

The ESSDAI domain scores will be calculated using the values presented in in [Table 8.6-2](#) for each domain separately.

Table 8.6-2: The EULAR Sjögren's Syndrome Disease Activity Index (ESSDAI) scoring algorithm

Domain	Score for activity level
Constitutional	No=0, Low=3, Moderate=6
Lymphadenopathy	No=0, Low=4, Moderate=8, High=12
Glandular	No=0, Low=2, Moderate=4
Articular	No=0, Low=2, Moderate=4, High=6
Cutaneous	No=0, Low=3, Moderate=6, High=9
Pulmonary	No=0, Low=5, Moderate=10, High=15
Renal	No=0, Low=5, Moderate=10, High=15
Muscular	No=0, Low=6, Moderate=12, High=18
Peripheral Nervous System (PNS)	No=0, Low=5, Moderate=10, High=15
Central Nervous System (CNS)	No=0, Moderate=10, High=15
Haematological	No=0, Low=2, Moderate=4, High=6
Biological	No=0, Low=1, Moderate=2

Information extracted from Table 1 in Seror R, Theander E, Brun JG, et al. Ann Rheum Dis, 2015;74:859–866. ³³

[REDACTED]

8.18 Counting rules for adverse events

8.18.1 At Subject Level

Where a subject has multiple adverse events within the same system organ class in a single analysis period, the subject will only be counted once at the system organ class level in adverse event frequency tables.

When a subject has the same adverse event, based on preferred terminology, reported multiple times in a single analysis period, the following criteria, in order of precedence, will be used to select the event to be included in summary tables:

- Relationship to study medication
- Intensity of event
- Onset date and time

When assessing relationship to study medication, relationship as reported by the investigator, events will be reported as related or not to study medication. Related events will take precedence over unrelated events in determining the event to include in summary tables.

More intense events will take precedence over less intense events in determining the event to include in summary tables.

Earlier onset date-time events will take precedence over late onset date-time events in determining the onset to include in summary tables.

When reporting adverse events by intensity, in addition to providing a summary table based on the event selection criteria detailed above, summary tables will also be provided based on the most intense event during the analysis period - independent of relationship to study medication. For these tables, the following criteria, in order of precedence, will be used to select the event to be included in summary tables:

- Intensity of event
- Onset date and time

Subjects will only be counted once in the ‘Total’ at their maximum intensity, regardless of SOC or PT.

8.18.2 At Event Level

At event level, each unique AE record will be counted. Unique AE record can be obtained by collapsing all AE records following a standard algorithm. The CRF data will be processed according to standard BMS algorithms to categorize each line of patient data as a new occurrence or a continuation of an existing event. This determination will be based upon onset and resolution dates. Each line of patient data will represent the maximum severity observed as well as the last known assessed relationship to study medication by the investigator.

